## **9.3 Definition of Populations**

Analyses of all outcomes will be done according to the intent-to-treat principle, that is, subjects will be analyzed in the treatment group to which they were randomized. To include all subjects in the primary analysis (including those who have only baseline assessments), our primary analysis will be a mixed model over all measurements (including baseline) with the restriction that the two groups have equal means at baseline (i.e. the primary analysis will be a constrained longitudinal data analysis). Missing data, which hinders the ability to perform a strict ITT analysis, is inevitable in this pragmatic trial. However, we will try to minimize the amount of missing data by following the National Research Council's recommendations on strategies for preventing missing data in clinical trials (e.g. try to collect outcome data on subjects who discontinue therapy). Also, we have incorporated into the analysis plan (section 9.6) several sensitivity analyses for assessing the impact of missing data on the results.

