## **9.6 Data Analyses**

Quantitative Analysis. As an estimate of uptake, we will present the proportion of patients who agree to be randomized out of all who are offered referral to treatment in our study. Randomization success will be assessed by side-by-side summaries of

baseline demographic and clinical characteristics of subjects by treatment group. Analyses of all outcomes will be done according to the intent-to-treat principle.

Primary Analysis. We will test and estimate the difference between COPES and CBT-CP in terms of BPI interference by using a linear mixed-effects model which simultaneously models all available BPI interference measurements including baseline. The model will contain fixed effects for treatment (categorical: COPES vs. CBT-CP), site (categorical), gender (categorical), time (categorical: baseline, 1, 4, 6, 12 months), and the treatment-by-time interaction. The only covariates that will be included in the primary and secondary analysis (including subgroup analyses) are site and gender. We are adjusting for these 2 variables because they are used for stratification in randomization. An unstructured variance-covariance matrix will be used to model correlations among repeated measures within a subject, and a therapist random effect will be used to model the correlation of outcomes in subjects who share the same therapist. Because this is a randomized trial, in the model above we will impose the constraint that the means for the two groups are equal at baseline (that is, we will perform a constrained longitudinal data analysis). Following the CONSORT recommendations, we will not perform any test for baseline differences as these tests are not needed in a randomized clinical trial “Such significance tests assess the probability that observed baseline differences could have occurred by chance; however, we know that any differences are caused by chance” This model will allow us not only to assess the between-group difference at 4 months (primary endpoint), but also to evaluate in secondary analyses whether between-group differences are maintained over time (at 6 and 12 months). Results will be summarized as least-squares means (and their 95% confidence interval) within and between groups. The primary analysis will be conducted at significance level 0.05.

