Tertiary Analysis Engagement/Dose/Completion. Patient engagement will be defined as a patient attending at least one session of CBT-CP or completing at least one treatment week of COPEs. Time from randomization to treatment, time from randomization to completion, completion (y/n, a binary variable) will be examined. For workload credit and co-payment billing purposes all sessions are recorded in the VA electronic health record. Study staff will collect session attendance data at the same time as they do the post-treatment chart review for adverse events. We will compare engagement, and completion between groups by using logistic generalized linear mixed models. Time to treatment and time to completion will be analyzed using Cox proportional hazards models. All models will include treatment, site and gender as fixed effects, and a random effect for therapist.

Recruitment Method: Patients will be recruited by 2 different approaches (provider referred or self-referred). We plan to examine potential differences in patient characteristics by recruitment type. First, we will present descriptive statistics for recruitment type in each treatment arm and overall in Table 1. If the sample sizes in the two recruitment type groups are sufficient ( $\geq 30$  in each group), we will include a supplemental table comparing the two groups on the baseline characteristics included in Table 1. We will compare baseline continuous characteristics using a t-test or Wilcoxon rank sum test, and categorical characteristics using the chi-square test or Fisher's exact test as appropriate.

Subgroup Analyses. To test whether between-group differences in outcome vary by gender, race/ethnicity comorbid substance use disorder, and alcohol use subgroup analyses will be performed via interaction tests. For example, to perform the race subgroup analysis for the primary outcome, we will enter race, the interactions race-by-time, race-by-treatment and race-by-time-by-treatment into the primary analysis models: the last two interactions will allow us to test whether race is a moderator of the treatment effect. We will perform subgroup analyses for the primary outcome and engagement. Subgroup analyses for other outcomes and subgroups (such as PTSD, depressive disorder) may be conducted as exploratory analyses.

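### The moderation test for BPI interference includes a moderator-by-treatment term, but the plan does not say that the equal-baseline constraint holds within moderator levels

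*Combined protocol and SAP*

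**What the plan says.** The primary analysis in section 9.6 is a constrained longitudinal model of all BPI interference measurements. Its fixed effects include treatment, site, gender, "time (categorical: baseline, 1, 4, 6, 12 months), and the treatment-by-time interaction". On the constraint it says "in the model above we will impose the constraint that the means for the two groups are equal at baseline". Section 9.3 describes the same model "with the restriction that the two groups have equal means at baseline". Both statements concern the two arms. Neither mentions arms within levels of a subgroup variable. Section 9.6 also declines to test baseline differences between arms, because randomisation leaves only chance to explain them.

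The Subgroup Analyses paragraph covers gender, race/ethnicity, comorbid substance use disorder and alcohol use, and takes race as its example: "we will enter race, the interactions race-by-time, race-by-treatment and race-by-time-by-treatment into the primary analysis models". It then says that "the last two interactions will allow us to test whether race is a moderator of the treatment effect". It does not say how the baseline constraint is coded once these terms are present. Nor does it say whether the test is joint over all visits or a contrast at 4 months.

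**The concern.** In a constrained longitudinal model the arms share one baseline mean, and by randomisation this is as true within each moderator level as overall. If baseline is a level of time and moderator-by-treatment enters as a free term, that term estimates how much the baseline arm gap differs between moderator levels. It carries no information about moderation of the treatment effect. Including it in the moderation test costs degrees of freedom, lets chance imbalance at baseline contribute to the result, and sits badly with the plan's own refusal to test baseline differences.

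This matters because interaction tests have little power to spare and these subgroups are not incidental. Section 4 gives a comparison of men and women as the reason for oversampling women to half the sample, and Aim 1 includes variation in outcomes across groups.

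**Working it through.** **Inputs from the documents.** Five categorical times (baseline and four follow-ups); SD 2.4; 305 evaluable per arm; half female; primary test at two-sided 0.05.

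**Assumptions, because the documents give no figure.** Subgroup tests at 0.05; complete data; no therapist effect; where a within-subject correlation ρ is needed, exchangeable with ρ from 0.4 to 0.7.

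**The plan's own figure.** The documents state no power or df for the subgroup test. The primary sample size reproduces: 2 × (1.960 + 0.842)² × 2.4² / 0.55² gives 299 per arm against 305 stated. Power at 305 is 80.8% for a difference of 0.55 and 90.0% for 0.63. 305/0.8 rounds up to 382 per arm.

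**Degrees of freedom.** A two-level moderator gives 2 × 5 × 2 = 20 cell means. With arms equal at baseline within each level, 2 × (5 + 4) = 18 are free. A free moderator-by-treatment term at baseline makes it 19. The joint test of the two interactions therefore has:

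| Moderator levels | Baseline term free | Constrained within level |
|---|---|---|
| 2 | 5 df | 4 df |
| 3 | 10 df | 8 df |
| 4 | 15 df | 12 df |

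The excess is k − 1.

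**Power.** The baseline contrast adds nothing to the noncentrality, so the same noncentrality is spread over more df. For two levels, a noncentrality of 11.94 gives 80% on 4 df and 76.6% on 5 df; about 7.5% more patients would recover the loss. Likewise 50% becomes 46.2%, and 90% becomes 87.7%. From 80%, three levels give 76.1% and four levels 75.7%.

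**Dependence on baseline imbalance, two levels.** The 5-df statistic equals the 4-df follow-up statistic plus z², where z is the standardised baseline interaction imbalance, and the two parts are independent. With no moderation, the rejection rate given z is P(χ²₄ > 11.07 − z²), and P(χ²₄ > x) = exp(−x/2)(1 + x/2).

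- z = 0: x = 11.07, giving 2.6%.
- z = 1.96: x = 7.23, giving 12.4%.
- z = 2.5: x = 4.82, giving 30.6%.

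In simulation at ρ = 0.5, trials with |z| > 1.96 were rejected 27% of the time by the 5-df test and 5.3% by the 4-df test. Over all trials the sizes were 5.05% and 5.02%.

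**Joint test or 4-month contrast.** Take ρ = 0.5 and scale the effect so that the constrained 1-df contrast at 4 months has 80% power (noncentrality 2.802² = 7.85). Given baseline, the follow-up covariance has diagonal 0.75 and off-diagonal 0.25.

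- Effect at month 4 only: 7.85 × 0.75 × 1.667 = 9.81. Power is 70.7% on 4 df and 66.8% on 5 df.
- Constant effect over follow-up: 7.85 × 0.75 × 4/1.5 = 15.70. Power is 90.6% on 4 df and 88.3% on 5 df.

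Across ρ from 0.4 to 0.7 the 5-df test loses 2 to 4 points against the 4-df test.

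**SE of a single 4-month contrast.** With 152.5 per cell the base SE is 2.4 × √(4/152.5) = 0.389. The variance factor is 1 − ρ² when constrained, 1 for the 4-month level with baseline free, and 2(1 − ρ) for change with baseline free. For ρ = 0.4 to 0.7 the SE is 0.356 to 0.278 constrained, 0.389 for level, and 0.426 to 0.301 for change. The excess is 9% to 40% for level and 20% to 8% for change. If reference coding keeps one moderator level constrained, the excess is roughly half: 5% to 22% for level and 10% to 4% for change.

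**The case against.** The strongest reply is that the plan never lifts the constraint. The subgroup terms go into the primary model, and that model itself lists a treatment main effect and then constrains baseline; nobody would say that the main effect reopens the baseline difference. If treatment is coded as zero at baseline, moderator-by-treatment and moderator-by-time-by-treatment span exactly the four follow-up contrasts. No df is wasted. Both terms are then needed, since the three-way term alone would miss moderation that is constant over follow-up. The plan's stance on baseline testing also makes a tested baseline term an unlikely intent.

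This stands as far as it goes: the text does not prove that the code will be wrong. It does not close the point, because the result turns on coding that the plan leaves open. In one natural alternative, treatment enters only through follow-up terms and moderator-by-treatment is then added as an ordinary categorical interaction. The two-level mean model then goes from 18 to 20 parameters (27 to 30 for three levels, 36 to 40 for four), and the overall baseline constraint is lost as well.

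It is also fair to say that the power loss and the SE penalty belong to different tests, a joint test and a single-visit contrast, and should not be added together.

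**Conclusion.** The point holds as a gap in specification with a defective literal reading. For a two-level moderator that reading costs 1 df and about 2 to 4 points of power, and it makes the chance of rejection depend on baseline imbalance. The df count and the conditional rejection rates need no value of ρ; the 4-month comparisons do. All rest on complete data and no therapist effect.

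A reader might infer four stronger things that the documents do not support.

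- That the plan definitely reopens the baseline difference. It leaves the coding unstated.
- That false positives are inflated. Overall type I error is 5% with or without the baseline term; only the rate conditional on imbalance changes.
- That a 4-month subgroup contrast will have an SE up to 40% larger. That needs a fully free baseline, the level at 4 months and ρ = 0.7, and the documents give no ρ.
- That the 4-month contrast must replace the joint test. The contrast is better when the effect is confined to month 4 (80% against 70.7% on 4 df) and worse when it is constant (80% against 90.6%).

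The scope is the primary-outcome subgroup analyses. Engagement is a binary outcome with no baseline measurement, so the issue does not arise there. The primary estimate and test are unaffected.

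**What to change.** Add to Subgroup Analyses in section 9.6 that arm means are constrained equal at baseline within each moderator level. The model then contains moderator and moderator-by-time, with treatment-by-moderator terms only at months 1, 4, 6 and 12. Report the treatment-by-moderator contrast at 4 months (k − 1 df), which matches the primary endpoint, alongside the joint follow-up test (4(k − 1) df), and state in advance which of the two is the main moderation test. The change needs SAP wording and model code only. It requires no new data and leaves the primary analysis as it is.

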#### Patterns of missing data

As a first step towards assessing the potential missing mechanism, we will examine the pattern of missing data and dropout in each treatment arm (both dropout from the therapy and dropout from participating in the survey). We will tabulate all missing data patterns and percent missing data at each time point by treatment arm. Additionally, we will examine missingness by reason for dropout. We will also plot mean outcomes over time by treatment group and time of last recorded measurement (i.e., subjects who have their last assessment at baseline, subjects who have their last assessment at 1 month, etc.). This will allow us to assess patterns in outcome prior to the last recorded measurement. An association between dropout and prior values of the outcome (e.g., those with worsening or non-improving pain more likely to drop out) will indicate a possible deviation from MCAR and that some of the missingness may be MAR.

Since it is not possible to distinguish between MAR and MNAR based on observed data, we will run our primary analysis under the MAR assumption (mixed model) and conduct sensitivity analyses to see how results change under different missing data assumptions.

### Baseline predictors of missing data

We will present and compare baseline characteristics (age, sex, race/ethnicity, mental and physical comorbidities) between those with missing outcome data at each follow-up time point (and at any timepoint) and those with available data. Comparisons will be done using t-tests and chi-square tests.

### Sensitivity analyses under MAR

If we find baseline variables not included in the original models to be associated with missingness (which would suggest that the MAR assumption was not reasonable for the original models), then we will conduct sensitivity analyses to gauge the effect of including those baseline variables as covariates in the mixed-effect models evaluating the difference between groups.

As a second sensitivity analysis under MAR, we will use multiple imputation based on chained equations (full conditional specification (FCS) imputation approach) to impute missing variables. The FCS approach is applicable to both monotone and intermittent missing data, and to both continuous and categorical variables. The imputation model will be more general than the analysis models and will include the primary/secondary outcomes measured at all time points, treatment group, all stratification variables and baseline variables. In order to use the EHR pain NRS data (measured at irregular intervals) in the imputation process, we will aggregate it at the monthly level (e.g. obtain a mean NRS for each subject and month). One hundred imputed datasets will be generated using PROC MI in SAS with the FCS method. Following Rubin's rule for multiple imputation inference, each of the simulated complete datasets will be analyzed by standard methods (using mixed models like those used for the primary analysis), and the results will be combined to produce results that incorporate missing-data uncertainty.

### Sensitivity analyses under MNAR

Further sensitivity analyses appropriate under MNAR such as pattern mixture models (PMM) will be examined. PMMs allow for the fact that subjects with different dropout patterns may have different response trajectories. We will implement PMM by including dropout pattern as a categorical variable in the primary analysis model, along with its interaction with all the other variables in the model. The dropout pattern variable will be defined based on the last recorded measurement; other definitions (e.g. based on reason from dropout) will be investigated. To get an estimate of the treatment differences from the PMM, we

will compute a weighted average of the treatment differences over the dropout patterns

The multiple imputation described above gives valid results only under a MAR assumption. We will also perform multiple imputation under MNAR under different assumptions. For example, we may assume that subjects who drop out early from the treatment in the experimental group (COPES) have worse BPI interference outcomes after dropping out than those who stay in the study by adding a shift of 0.5 points to their MAR-imputed outcome. We would then vary the assumption about the shift after dropping out in both treatment groups and identify which of these assumptions would change the conclusion from our primary analysis.

Responder analysis (exploratory analysis). Response will be defined as at least a 30% improvement in BPI interference score from baseline to 4 months. Reduction in pain/interference of 30% or more has been shown to be clinically meaningful and is recommended by IMMPACT that the percentage of participants who receive this reduction be reported in all clinical trials of chronic pain treatments. We will investigate predictors of response by using both logistic regression and classification trees, as classification trees can accommodate a larger number of predictors (including high order interactions) than the typical logistic regression. Predictors considered will include treatment, gender, race, baseline BPI interference and other baseline variables such as comorbidities.

Propensity score exploratory analysis. If the sample size allows, we will perform an analysis of the primary outcome (4-month BPI interference) that takes into account the type of treatment received in the synchronous CBT-CP group, that is, the treatment variable will be a 3-level categorical variable: video/telephone CBT-CP, in-person CBT-CP and COPES. This analysis will allow us to compare the two types of CBT-CP against each other and separately against COPES. To balance these three groups in terms of baseline covariates, we will use inverse probability of treatment weighted estimation based on propensity scores. The weights will be estimated from generalized boosted models and the estimates will represent population average treatment effects. At a minimum, the propensity models will include demographics, baseline values of the outcomes, and baseline medical and mental health comorbidities. Balance among treatment groups will be evaluated by standardized differences, with values >0.1 indicating imbalance. To deal with missing data, this analysis will be applied to multiple imputed datasets (see Missing Data Sensitivity Analyses section).

Resource Use. *Intervention Costs.* Therapists will use a log to record time spent in intervention-related activities for all treatment days. Therapists will record this information on the IVR system's therapist interface using an online calendar that has mandatory data fields for this information. We will regularly review completion of this field during monthly quality assurance monitoring with weekly checks in the first month of the treatment during the trial and the first month of any new therapist's tenure. A random sample of 20% of all treatment days will be used in the estimation of personnel costs. Time records will be combined with wage data from the VA Financial Management System to estimate intervention-specific personnel costs. Technology costs of the COPES IVR program include fixed costs (e.g., software development and computer maintenance) plus variable costs (e.g., minute costs for IVR calls). One-time fixed start-up costs will be reported separately. *VA Inpatient and Outpatient Service Use* data will be obtained from the Musculoskeletal Diagnoses Cohort (MSD), a project currently underway as part of the VA Connecticut Healthcare System's CREATE. The MSD is developing validated algorithms for using VA electronic health record data to identify utilization events, comorbid conditions, receipt of opioid medications, and pain screening results, for patients with pain-related diagnoses.

Intensity of Service Use. As exploratory analyses, we will compare service utilization during the 12 months post-baseline by category (e.g., dose of opioid medication dispensed (continuous variable), number of PCP visits (count), non-opioid medication dispensed (binary), non-pharmacological pain care (binary), use of emergency department (binary) and urgent care (binary)) between groups using linear/generalized linear mixed models with an appropriate outcome distribution. We will also consider two-parts models for the opioid dose and PCP visits outcomes in case of zero-inflation. We will conduct a budget impact analysis and will include the cost of the intervention (personnel, supplies, CBT therapist training, and IVR fixed/variable costs) as well as costs for specific medical care services likely to be affected. Data from CBT therapists time records will be combined with wage data from the VA Financial Management System to produce estimates of intervention-specific personnel costs. Costs associated with the use of specific medical care services, such as medications, will be obtained from the VA Managerial Cost Accounting (MCA) System. Cost analysis will be conducted in accordance with the guidance provided by Sullivan et al. including the use of sensitivity analysis and scenarios that allow for varying assumptions about intervention uptake, compliance or component costs. All resource use and cost comparisons will be adjusted for any observed differences in baseline characteristics. Because costs of resource utilization are usually skewed, alternative modeling techniques (e.g., log-transformed costs, negative binomial regression)

will be used. Information on non-VA care will be collected by automated IVR call assessment. To mitigate recall bias, we will use a two-time frame method that asks about utilization over the past 6 months and over the past 2 months with more weight given to the shorter timeframe.

Process evaluation. In order to refine and evaluate our implementation of the proposed interventions, we will conduct a formative evaluation, with implementation-focused, progress-focused, and interpretation phases. We will use semi-structured telephone, or in-person interviews conducted by a trained research assistant under the supervision of a qualitative expert. Interview guides will be developed using constructs and questions derived from the Consolidated Framework for Implementation Research (CFIR), refined based on our experience in the COPES implementation trial and tailored to the informant group being interviewed (mental health provider, primary care provider or administrator). The interview guides are being developed and piloted in the context of another approved study and when complete, the guides will be submitted to the cIRB for approval prior to use. Interviews will be audio-recorded and professionally transcribed by a VHA-approved contractor. Participants in each of the stakeholder categories (i.e., providers and administrators) will be recruited by in-person recruitment strategies or email solicitations with the assistance of the WH-PBRN site lead. Staff interviews will be conducted with clinical staff who provide clinical care and who we anticipate will be directly involved in patient referral including primary care providers (n=2 per site), mental health providers (n=2 per site), and administrators (n=2 per site). Providers will be emailed an information sheet or asked to view it on the study website which details their participation. Interviewers or staff will go over this with the provider participant and will specifically ask about consenting to the audio recording of their voice. We will record the provider's confirmation of this consent.

Qualitative analysis. We will utilize data reduction strategies to sort, focus, discard and organize data to draw inferences regarding the implementation interventions in place at each facility. We will develop a template summary of data at each facility according to a small set of pre-determined domains that align with the interview guides developed for each group of respondents. Once we have developed that summary for each facility, we will create a matrix across all facilities to understand the major issues with regards to implementation. Matrices streamline the process of noting, simultaneously and systematically, the similarities, differences and trends in response across a group of informants. All interviews and focus groups will be digitally recorded for verbatim transcription (either transcribed by the transcription service previously described or through VA MS Teams software and reviewed by study staff). Analysis of qualitative data will be

conducted using ATLAS.ti, a qualitative data analysis software program allowing fluid interaction of data across types and sources.

Examination of key components of the facilitation approach. Using CFIR domains and constructs we will systematically consider strengths and weaknesses of our implementation strategy in the formative evaluation. We will collect qualitative and quantitative data prior to, during, and at completion of the COPES ExTRA study. We will use the RE-AIM framework to evaluate the summative success of the COPES and CBT-CP implementation. Reach will be evaluated by determining the refusal rate (percentage of those patients for whom an alert was triggered but the referral was not made and demographic characteristics of Veterans who participate versus those who do not). Refusal rates will be calculated overall and for each site.

Efficacy/Effectiveness measures are described elsewhere (BPI interference is the primary effectiveness measure). Adoption is defined as the proportion of providers at each site who report willingness to refer to the interventions and their representativeness. We will also examine demographic and qualitative formative evaluation data associated with high and low adopting sites. Implementation: We will use qualitative formative evaluation data to understand the implementation process in the study sites. We will query site staff and/or review patient EHR to determine treatment format (i.e. individual, group). Maintenance will be evaluated by examining COPES and CBT-CP 12 month outcomes. To assess system level maintenance, we will review qualitative formative evaluation data to identify potential barriers to maintenance trajectories of provider referral rates over time, and necessary areas for additional assistance.

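### As written, the pattern-mixture sensitivity analysis cannot give an overall month-4 treatment difference, because patterns ending at baseline or month 1 hold no month-4 data

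*Combined protocol and SAP*

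**What the plan says.** Section 9.6 (Primary Analysis) specifies a linear mixed model with fixed effects for treatment, site, gender, "time (categorical: baseline, 1, 4, 6, 12 months), and the treatment-by-time interaction". The two arms are constrained to have equal means at baseline. The endpoint is BPI interference at month 4 (Section 9.5.1).

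The pattern-mixture analysis (Section 9.6, Sensitivity analyses under MNAR) builds on that model:

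- The model: "We will implement PMM by including dropout pattern as a categorical variable in the primary analysis model, along with its interaction". The sentence extends the interaction to every other model variable.
- The patterns: "The dropout pattern variable will be defined based on the last recorded measurement". The plan adds that "other definitions (e.g. based on reason from dropout) will be investigated", but specifies none of them.
- The estimate: the analysts "will compute a weighted average of the treatment differences over the dropout patterns". A citation is attached, but no weights are given.

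The subsection Patterns of missing data lists the groups this definition produces: "subjects who have their last assessment at baseline, subjects who have their last assessment at 1 month, etc". Section 9.3 keeps people with only a baseline assessment in the primary analysis, so the baseline-only pattern exists by design.

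The MNAR subsection also plans a second approach. Multiple imputation adds a shift (0.5 points is the example) to imputed values after dropout, and the shift is then varied in both arms to find where the conclusion changes.

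**The concern.** A pattern-mixture model estimates the treatment difference within each dropout pattern and then averages. Here the quantity wanted is the month-4 difference. Someone whose last measurement is at baseline or month 1 has no month-4 value by definition. With categorical time and full interactions, each pattern has its own free month-4 means, so for these two patterns nothing in the data or the model supplies them. The usual remedy is an identifying restriction that says where the missing means come from, or a pooling of patterns. The plan states neither.

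The analysis would therefore stop at the averaging step, and a number could be obtained only through a choice not written down in advance. The people it fails to cover are those an MNAR analysis is meant to address. A convenient repair that drops the empty patterns would leave them out and could be read as support for the MAR result.

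**Working it through.** **1. The plan's own figures.** Section 9.2 gives SD 2.4, difference 0.55, two-sided 0.05, 305 per group and 20% attrition. The usual two-sample formula gives 299 per arm for 80% power. At 305 per arm, power is 0.808 for 0.55 and 0.900 for 0.63. Attrition: 305 / 0.80 = 381.25, rounded up to 382 per arm, or 764 in total. The sample size reproduces and is not in question.

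**2. Which cells can be observed.** A participant in a given pattern can contribute only visits up to the last measurement:

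| Last measurement | Visits that can be observed | Month 4 present? |
|---|---|---|
| Baseline | 0 | No |
| Month 1 | 0, 1 | No |
| Month 4 | 0, 1, 4 | Yes |
| Month 6 | 0, 1, 4, 6 | Yes |
| Month 12 | 0, 1, 4, 6, 12 | Yes |

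Over two arms this gives 2 × (1 + 2 + 3 + 4 + 5) = 30 observable pattern-by-arm-by-visit cells.

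**3. Estimability.** A contrast L is estimable if it lies in the row space of the design matrix X, that is, if L·X⁺·X = L, where X⁺ is the pseudoinverse. X holds the pattern, treatment and time terms over the 30 cells. Site, gender, the therapist random effect and the within-subject covariance are left out because they supply no information on a treatment contrast at an unobserved visit.

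For the model as written, the columns are 25 pattern-by-time means plus 20 post-baseline treatment effects (5 patterns × 4 visits), 45 in all. The data support 15 of the means and 0 + 1 + 2 + 3 + 4 = 10 of the effects, so the rank is 25. Other readings were tested in the same way:

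| Reading | Month-4 difference estimable, by last visit 0 / 1 / 4 / 6 / 12 | Average over all patterns |
|---|---|---|
| As written: categorical time, full interactions, equal baseline means | no / no / yes / yes / yes | not estimable |
| Same, without the baseline constraint | no / no / yes / yes / yes | not estimable |
| Two-way pattern interactions only, constraint kept | no / yes / yes / yes / yes | not estimable |
| Linear time, full interactions, with or without the constraint | no / yes / yes / yes / yes | not estimable |
| Two-way interactions only and constraint dropped | yes / yes / yes / yes / yes | estimable |

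The last reading departs from the primary model and works only by assuming one treatment-by-time effect common to all patterns. Every reading that keeps the baseline constraint fails.

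**4. How many people.** 764 − 610 = 154, and 154 / 764 = 20.2%, or 77 per arm. This assumes that all planned attrition falls before month 4 and is permanent.

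**5. What is left undetermined (illustration; the effects are assumed).** Suppose the estimable patterns carry 80% of the weight and have a difference of 0.55, and the early-dropout patterns have an unknown difference d:

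overall = 0.80 × 0.55 + 0.20 × d = 0.44 + 0.20d

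| d | Overall | Renormalised over estimable patterns |
|---|---|---|
| −0.55 | 0.33 | 0.55 |
| 0 | 0.44 | 0.55 |
| 0.55 | 0.55 | 0.55 |
| 1.0 | 0.64 | 0.55 |

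The renormalised figure is (0.80 × 0.55) / 0.80 = 0.55 whatever d is.

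**The case against.** The lack of month-4 data in the two early patterns is hard to dispute. The case on the other side concerns what follows from it, and much of that case stands.

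- **A reader might infer that the analysis collapses to those who stayed.** The plan does not say so. Nowhere does it tell the analyst to drop patterns or renormalise weights. Followed literally, the software reports the contrast as not estimable, which is a visible failure. The restricted result needs a further, unplanned step.
- **A reader might infer that the trial has no usable MNAR check.** It does. The shift-based imputation in the same subsection supplies month-4 values for early dropouts and is varied in both arms as a tipping-point analysis.
- **A reader might take 154 as the expected count, or take the illustration as a fixed overstatement.** Neither is supported. Section 9.6 expects intermittent gaps, and someone who misses month 4 but answers later falls in an estimable pattern. The documents give no split between permanent and intermittent missingness. Renormalising could overstate, match or understate the overall effect, depending on d.
- **The wording is partly open.** Other pattern definitions are to be looked at, and one based on reason for dropout could be estimable if each group contained month-4 data. The cited source for the averaging step may define weights or pool patterns, but that cannot be known from these documents. Neither possibility completes the analysis that the plan says will be implemented.

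**Conclusion.** The point holds for the pattern-mixture analysis as described in Section 9.6. With categorical time, patterns by last measurement and full interactions, the month-4 difference is not estimable in the baseline and month-1 patterns, so the planned weighted average cannot be computed. This conclusion does not depend on the size of the weights, only on some weight falling on those patterns. Up to about 20% of participants could be in them, on the assumption that planned attrition is all permanent and before month 4.

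The defect is confined to one sensitivity analysis. The primary analysis, the sample size and the shift-based imputation stand. It still merits correction, because this is a stated analysis that fails when followed, and the repair should be chosen before anyone has seen results by arm.

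**What to change.** Before unblinding, revise the pattern-mixture paragraph of Section 9.6 so that the month-4 difference is identified in every pattern, in one of two ways:

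- State an identifying restriction by arm, for example complete-case or neighbouring-case values, implemented by imputation, with a rule for intermittent gaps; or
- Pool patterns so that each pooled group contains month-4 data, and acknowledge the assumption that early dropouts then share the treatment difference of those they are pooled with.

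In either case:

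- State the pattern weights.
- State whether equal baseline means are imposed within patterns. Pattern is a post-randomisation grouping, so randomisation does not guarantee equality within it.
- Rule out renormalising over the estimable patterns only.
- Report the result beside the shift and tipping-point analysis already planned.

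The cost is SAP wording and modest extra programming, with no new data. The downside is reliance on an assumption that cannot be tested, which any MNAR analysis carries and which would now be stated.
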